Using G-power software (version 3.1.9.7; Franz Faul, Universitat Kiel, Germany) for windows and regarding MANOVA study, alpha level of 0.05, confidence level 0.80, and effect size 0.56, calculated from the previous study of (**Agirman et al., 2017**) that used the isokinetic dynamometer for measuring the peak torque of wrist with a sample of 35, and a two-sided alternative hypothesis, the sample size is 39 patients to be able to reject the null hypothesis. If 15% dropout rate is anticipated, approximately 44 patients (twenty-two in each group) will be recruited.

1. Students' selection:

The current study will be conducted on twenty-two non-specific neck pain Egyptian physical therapy students a with referral from orthopedic surgeons by diagnosis with non-specific neck pain other twenty-two without neck pain subjects from outpatient clinic of Faculty of Physical Therapy, EL DELTA University. Students' age ranges from 18 to 23 years. Students will be selected from faculties of physical therapy. Students will be assigned into two equal groups, the study group (GA) (chronic non-specific neck pain students) and the control group (GB) (normal students). They will be instructed not to participate in any training program until the posttest.

Inclusion criteria:

- 1- Students from both genders (**Fayez, 2014**).
- 2- Duration of the non-specific neck pain is more than 3 months (for symptomatic group with no neurological manifestations and with referral from orthopedic surgeons by diagnosis with non-specific neck pain) and for matched students, they do not have any history of neck pain (**Chung & Jeong, 2018**)
- 3- Student' age ranges from 18 to 23 years.
- 4- Neck pain intensity on the numerical Pain Rating Scale will be between 3 to 8.
- 5- Neck pain-related disability on the Neck Disability Index will be between 5-14points (10 – 28%) mild disability and 15-24points (30-48%) moderate disability.
- 6- Body mass index for students will not be less than 18.5 and not more than 29.5 (**Alasadi, 2018**).

Exclusion Criteria:

Any participant suffered from one of these symptoms will be excluded:

- 1- Indications of neurological conditions (i.e., Parkinson's disease, multiple sclerosis, head injury, peripheral neuropathy, stroke, or nerve root entrapment) (**Mahmoud et al., 2020**).
- 2- Headache caused by a certain diagnosis of headache.
- 3- History of cancer, infection, or any other illness symptoms.

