- 4- History of trauma, whether it was accompanied or not by structural issues with the neck, shoulder, or head (such as whiplash) within the last 12 months or any traumatic spinal cord injury (**Park et al., 2016**).
- 5- Any known cardiovascular problems or cerebrovascular insufficiency symptoms.

- 6- Any known musculoskeletal disorder (i.e., joint replacement, amputation, physically limiting arthritis, contractures of fixed deformity or muscular dystrophy) which limits physical daily activities (**Bidja et al., 2018**).
- 7- History of orthopedic or neurological conditions such fractures, surgeries on the upper limb or hand, carpal tunnel syndrome, De Quervain's syndrome, or diabetic mellitus that result in functional defects of the hand strength (**Fayez, 2014**).
- 8- Specific diagnosis of the cervical spine spondylosis, disc prolapse, spinal stenosis, cervical fracture, etc.
- 9- Subjects are also excluded if they have had any recent (within the last three months) treatment for neck pain (**Park et al., 2016**).
- 10- Any medical condition affecting the sensory system (visual, auditory and speech problems).
- 11- Students are also excluded if they have had forward head posture.

2. Instrumentations

For Measurement and Assessment

- Photogrammetry posture analysis forward head (by the smartphone application forward head posture (FHP) as exclusion screening procedure to exclude subjects with abnormal forward head).
- Numerical Pain Rating Scale
- Arabic version of the Neck Disability Index (NDI)
- Arabic version of the Fatigue Severity Scale
- Isokinetic dynamometer

a) Photogrammetry posture analysis forward head:

Intra-rater reliability of the mobile application forward head posture had an intraclass correlation coefficient of 0.88. The inter-rater reliability generated an intraclass correlation coefficient of 0.83 to 0.89. Criterion validity data were

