above 0.82. The minimum detectable change was 4.96 for intra-rater and 5.52 for inter-rater reliability. The smartphone application exhibited 94.4% sensitivity and 84.6% specificity. The smartphone application forward head posture is a valid and reliable tool to measure craniocervical angle (CVA) in a standing position and, therefore, could be a useful assessment tool in clinical practice (**Gallego-Izquierdo et al., 2020**). The CV angle is the best indicator of FHP (**ShaghayeghFard et al., 2016**). An angle less than 50-53 may indicate FHP (**Lee et al., 2015**). Thereby, the smaller the CV angle, the greater the disability (**Cheung et al., 2009**).

b) Numerical Pain Rating Scale (NPRS):

Numeric Pain Rating Scale (NPRS) has shown high test-retest reliability and for construct validity, the NPRS has shown to be highly correlated with the VAS in patients with rheumatic and other chronic pain conditions (pain>6 months) (**Young et al., 2019; Sharma et al., 2017**) (**Appendix II**).

c) The Neck Disability Index (NDI):

The Neck Disability Index (NDI) demonstrated excellent internal consistency and good test-retest reliability. Content validity was confirmed as no floor or ceiling effects were detected for the Neck Disability Index (NDI) total score. Construct validity was established with factor analysis revealing two-factor subscales explaining 66% of the variance. The Neck Disability Index (NDI) showed a strong correlation with a visual analog scale (VAS) and a moderate correlation with the global rating of change (GROC) (**Lim et al., 2020; Young et al., 2019**) (**Appendix III**).

The Neck Disability Index (NDI) (modification of the Oswestry Low Back Pain Disability Index). Patient-completed, condition-specific functional status questionnaire with 10 items including pain, personal care, lifting, reading, headaches, concentration, work, driving, sleeping and recreation. The NDI has

sufficient support and usefulness to retain its status as the most used self-report measure for neck pain. The NDI can be used to evaluate the patient's status presence and to evaluate the evolution during the therapy.

d) The Fatigue Severity Scale (FSS):

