- All the subjects will be included according to inclusion and exclusion criteria and they will be selected from outpatients clinics of EL DELTA University. Then, after taking their individual demographic data, they will be assigned into two groups, the study group (GA) (chronic non-specific neck pain subjects without neurological manifestations) and the control group (GB) (normal subjects). After that, they will sign an informed consent form after receiving a brief orientation session about the nature of the study, the study purpose, procedure, possible benefits, and risks with preserving each subject privacy.

Measurement of craniocervical angle to exclude subjects with abnormal forward head posture

Non-specific neck pain students will be evaluated to assess forward head posture by photographic posture analysis method by placing two markers on the ground separated by 1.5 m, where the smartphone and the subject will be located. Reference markers will be placed on the spinous process of C7 and in the swallow of the subjects' ears, which will be identified through palpitation. The subject will be placed on the floor mark, barefoot and standing, lateral to the evaluator. At this point. The evaluators will be experienced and trained physiotherapists (**Gallego-Izquierdo et al., 2020**). The ones calculated with the FHP app will be classified attending to the presence or not of FHP. The presence of FHP (FHP group) will be determined by an angle value lower than 50, and the absence of FHP (no-FHP group) if the angle value will be greater than or equal to 50 (**Lee et al., 2015**).

Assessment of pain intensity by Numerical Pain Rating Scale

Also they will be evaluated to assess pain intensity by Numerical Pain Rating Scale (**Appendix II**) as The Numeric Pain Rating Scale (NPRS) is a unidimensional measure of pain intensity in adults, including those with chronic pain due to rheumatic diseases. (man in pain, R) The NPRS is a segmented numeric version of the visual analog scale (VAS) in which a respondent selects a whole number (0–10 integers) that best reflects the intensity of his/her pain. The 11-point numeric scale ranges from '0' representing one pain extreme (e.g., "no pain") to '10' representing the other pain extreme (e.g., "pain as bad as you can imagine" or "worst pain imaginable"). As inclusion criteria, Neck pain intensity on the numerical Pain Rating Scale will be between 3 to 8.

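### Forward head posture excludes any participant, but the only described measurement names the neck-pain students; screening of controls is undescribed, a selection-bias risk of unknown size

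*Combined protocol and SAP*

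**What the plan says.** All references are to the combined protocol and SAP unless noted.

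- **Exclusion Criteria, opening line:** "Any participant suffered from one of these symptoms will be excluded". Item 11: "Students are also excluded if they have had forward head posture". Neither is limited to a group.
- **2. Instrumentations, list:** the posture app is included "as exclusion screening procedure to exclude subjects with abnormal forward head", again with no group named.
- **Participant preparation:** "All the subjects will be included according to inclusion and exclusion criteria". The same paragraph then divides participants into study and control groups.
- **Measurement of craniocervical angle, the next subsection:** "Non-specific neck pain students will be evaluated to assess forward head posture by photographic posture analysis method". Forward head posture "will be determined by an angle value lower than 50".
- **2. Instrumentations, a):** "The smartphone application exhibited 94.4% sensitivity and 84.6% specificity", and "Thereby, the smaller the CV angle, the greater the disability".

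No section describes photographing controls, and none says they are exempt. In the separate SAP document, Table (1) compares age, weight, height and BMI for 44 students but does not give the craniovertebral angle.

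**The concern.** This is a cross-sectional comparison without randomisation, so its validity depends on selecting the two groups in the same way apart from neck pain. The protocol considers forward head posture important enough to exclude, and it links a smaller angle to greater disability. If only the neck-pain students are measured, the factor is largely removed from that group and left at its natural frequency among the controls.

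The planned analysis would not reveal this. Neither the protocol's Statistical Analysis section nor the SAP's data analysis section adjusts for posture, and the baseline table does not show it.

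**Working it through.** **Step 1: set the text side by side.** Who is excluded: any participant. Who is measured: the neck-pain students. Three features favour reading the second literally.

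1. The groups have been split in the paragraph just before, so naming one of them looks specific.
2. The pain and Neck Disability Index steps that follow continue with the same people and apply entry ranges (pain 3 to 8, index 5 to 24 points). Controls with no history of neck pain cannot be expected to meet these.
3. Where both groups are meant, the protocol says so: the isokinetic testing is explicitly assigned to the subjects of both groups.

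**Step 2: illustrate the possible size.** The plan states no figure to reproduce.

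*Inputs from the protocol:* sensitivity 0.944, specificity 0.846, 22 per group.

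*Assumptions, not in the documents:* prevalence p of forward head posture of 20%, 40% or 60%, equal in both groups before screening; posture lowers an outcome by 0.3 or 0.5 SD; the stated accuracy applies at the below-50 cut-off.

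*Formulas:*
- Residual in the screened group: r = p × 0.056 / [p × 0.056 + (1 − p) × 0.846]
- Shift = (p − r) × assumed effect
- Standard error of the standardised difference = √(2/22) = 0.30

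For p = 0.2: r = 0.0112 / (0.0112 + 0.6768) = 1.6%. For p = 0.4: 0.0224 / 0.5300 = 4.2%. For p = 0.6: 0.0336 / 0.3720 = 9.0%.

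| p | Expected in 22 screened cases | Expected in 22 unscreened controls | Shift at 0.3 SD | Shift at 0.5 SD | False-positive rate at 0.5 SD, no true difference |
|---|---|---|---|---|---|
| 20% | 0.4 | 4.4 | 0.06 | 0.09 | 0.060 |
| 40% | 0.9 | 8.8 | 0.11 | 0.18 | 0.089 |
| 60% | 2.0 | 13.2 | 0.15 | 0.25 | 0.131 |

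The last column is from a two-sided t test at 0.05 with 42 degrees of freedom and noncentrality shift/0.30. With no posture effect, the shift is 0 and the rate stays at 0.05.

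**Step 3: direction.** Let δ be the true deficit in the neck-pain group and b the shift. The expected observed deficit is δ − b. It lies closer to zero than δ only when δ exceeds b/2. When δ = 0, controls look weaker by b, which is a spurious difference.

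**Step 4: sensitivity to equal prevalence.** Controls have no history of neck pain. If posture tracks neck pain, they may have less of it. With an assumed 60% in cases and 10% in controls, the imbalance is 10% − 9.0% = 1.0 percentage point, and at 0.5 SD the shift is only 0.005 SD.

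**Step 5: cost of screening controls.** Share screening positive = 0.944p + 0.154(1 − p) = 31%, 47% or 63%. Candidates for 22 places: 22/0.688 = 32, 22/0.530 = 42, 22/0.372 = 59. If controls already tested were restricted afterwards, about 15, 12 or 8 of 22 would remain. The standard error √(1/22 + 1/n) would rise from 0.30 to 0.33, 0.36 or 0.41.

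**The case against.** The eligibility rule itself is common to both groups. The exclusion list, the instrument list, the general eligibility statement and the subsection's own heading all speak of participants or subjects without distinction, and the word only never appears. Group labels are loose elsewhere too: the pain and disability inclusion criteria carry no group label, although controls could not meet the pain range. The sentence may therefore be careless drafting, and controls may have been screened.

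Bias also requires that some controls had forward head posture and that posture affects wrist torque or fatigue. The documents give no figure for either. The disability statement does not mention the wrist, and the introduction reports an opinion that forward neck posture is unrelated to pain in adolescents. Every shift in the illustration is smaller than its standard error.

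Most of this stands. It rules out saying that the groups have different eligibility criteria or that the comparison is shown to be biased. It does not remove the gap: the one operational instruction names one group, and nothing tells staff to apply it to the other. A shift below one standard error is also not harmless, since it is systematic and at the upper end of the illustration more than doubles the false-positive rate.

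**Conclusion.** The exclusion criterion and the screening procedure do not match and must be reconciled. Followed as written, forward head posture is screened out by measurement in the neck-pain group only, which creates a selection-bias risk of unknown size. The 0.06 to 0.25 SD range is an illustration that rests on assumed prevalence, an assumed effect on wrist outcomes, equal prevalence before screening, and the app's accuracy holding at the cut-off. The true value could be zero.

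A reader might infer three stronger things that the documents do not support:

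- **That the comparison is biased.** They do not say that controls went unscreened, and they give no posture effect on the wrist.
- **That the bias runs toward no effect.** This needs both a posture effect and a true deficit larger than half the shift. Without a true deficit, the same imbalance inflates false positives.
- **That the non-significant fatigue results in the SAP hide a real deficit.** Nothing reported there allows this to be checked.

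**What to change.** Amend the procedure sentence so that all students of both groups are evaluated for forward head posture, with the same app, the same evaluators and the cut-off the procedure already states, before enrolment in either group. Record the angle for everyone and report it by group.

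The SAP already reports 44 students, so the wording change alone may come too late for these data:

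- If controls were screened, state so; that resolves the eligibility question, and the angle should still be reported by group.
- If they were not, state it as a limitation. If their angle can still be measured, report it by group and give a comparison restricted to those meeting the criterion as a sensitivity analysis only. A later angle is not the angle at testing, and the protocol puts the minimum detectable change at about 5 (4.96 intra-rater, 5.52 inter-rater).

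The app and evaluators are already in place. The real cost is recruitment: about 32 to 59 control candidates for 22 places under the assumptions above. A restricted re-analysis would lose power, with roughly 15 to 8 controls left.
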